**PROTOCOL VERSION SUMMARY OF CHANGES TABLE**

[figure not shown]

**1. PROTOCOL SUMMARY****1.1. SYNOPSIS****Protocol Title:**

A multicenter, open-label, extension trial to investigate long term efficacy and safety of lonapegsomatropin in adults with growth hormone deficiency

**Trial Rationale:**

To assess the long-term safety of once-weekly lonapegsomatropin in adults with growth hormone deficiency (GHD/AGHD) who participated in trial **TCH-306**.

**Objectives and Key Endpoints:**

| Objectives   | Key Endpoints   |
|--|---|
| Primary   |   |
| 
 
To evaluate the safety of once-weekly lonapegsomatropin in adults with GHD previously treated in trial TCH-306
 
 | 
Safety endpoints as measured throughout the treatment period:
 
 
Adverse events (AEs)
 
Laboratory values
 
Vital signs
 
Immunogenicity
 
12-lead electrocardiogram (ECGs)
 
Fundoscopy
 
 |
| Secondary 
 
To evaluate the efficacy of once-weekly lonapegsomatropin in adults with GHD
 
                  | 
At Week 52 (as assessed by dual-X-ray absorptiometry (DXA)):
 
 
Trunk percent fat
 
Trunk fat mass
 
Total body lean mass
 
   |

**Overall Design:**

This is a phase 3 open-label multicenter extension trial designed to evaluate the long-term safety and efficacy of lonapegsomatropin administered once-weekly. The trial participants are adults (males and females) with confirmed GHD having completed the treatment period in trial TCH-306 (foresiGHt).

**Brief Summary:**

The purpose of this trial is to assess long-term safety of lonapegsomatropin in participants who completed the treatment phase of trial **TCH-306**. Participants are adults with GHD previously treated with either lonapegsomatropin, a daily somatropin product, or placebo.

Trial details include:

- Trial duration will be up to 60 weeks
- Screening Period up to 3 weeks
- Treatment duration will be 52 weeks
  - Titration period 12 weeks
  - Maintenance period 40 weeks
- Follow-up period 30-37 days (approx. 4-5 weeks)
- Visit frequency will be every 4th week during titration, four visits during maintenance period, and two during follow-up. Two visits are remote (phone/web).

**Number of Participants:**

Participants who completed the treatment period of trial TCH-306 and meet eligibility criteria can be included in the trial. The sample size in trial TCH-306 is approximately 240.

**Intervention Groups and Duration:**

- Total duration of trial participation for each participant will be 60 weeks, up to 3 weeks for screening, 52 weeks on treatment and up to 37 days for follow up
- Route of administration is subcutaneous (sc) injections
- Dose regimen is once-weekly
- Starting dose depending on age and oral estrogen use, fixed titration period, with individual dose changes/adjustments if warranted due to AEs or IGF-1 values
- Participant safety and IGF-1 results will be continuously monitored by the medical monitors.

## 1.2. SCHEDULE OF ACTIVITIES (SOA)

| Timing   | Screening Visit  | V8  | Titration Period            |              |                    | Maintenance Period |                               |                               | End of Treatment   | Follow-up                                |                            |
|--|--|---|-----------------------------|--------------|--------------------|--------------------|-------------------------------|-------------------------------|--------------------|--|----------------------------|
|  |  |   | V9 week 4                   | V10 week 8   | V11 week 12        | V12 week 17        | V13 week 28                   | V14 week 38                   |                    | V15 week 52                              | V16 Safety                 |
| Procedure  | Screening Visit and Screening Procedures should be performed unless the subject can be dosed at V8 ≤8 weeks after TCH-306 V7. Subjects may not be re-screened if they failed eligibility criteria at V7. | ≤3 weeks after Screening Visit or TCH-306 V7 j | 3 weeks + 4-5 days after V8 | Remote visit | 4-5 days post dose | 4-5 days post dose | 1-3 days (8-75 hrs) post dose | 1-3 days (8-75 hrs) post dose | 4-5 days post dose | Remote visit, 14-16 days after last dose | 30-37 days after last dose |
| Informed consent a  | Before or at Screening Visit   |   |                             |              |                    |                    |                               |                               |                    |  |                            |
| Inclusion and exclusion criteria i                        | X i   | X i  |                             |              |                    |                    |                               |                               |                    |  |                            |
| Physical examination   | X  |   |                             |              | X                  |                    |                               |                               | X                  |  |                            |
| Weight   | X  |   |                             |              | X                  |                    |                               |                               | X                  |  |                            |
| Pregnancy test (females of childbearing potential only) b | X  | X   | X                           |              | X                  | X                  | X                             | X                             | X                  |  | X                          |
| Safety laboratory tests c                                 | X  |   | X                           |              | X                  | X                  | X                             | X                             | X                  |  |                            |
| IGF-1 and IGFBP-3 laboratory tests c                      | X  |   | X                           |              | X                  | X                  | X                             | X                             | X                  |  |                            |
|  |  |   |                             |              |                    |                    |                               |                               |                    |  |                            |
| ADA/Antibody laboratory test   | X  |   | X                           |              | X                  | X                  | X                             | X                             | X                  |  | X                          |
| DXA (dual-X-ray-absorptiometry) scan                                 |  |   |                             |              | X d     |                    |                               |                               | X d     |  |                            |
| 12-lead ECG  | X  |   | X                           |              |                    |                    |                               |                               | X                  |  |                            |
| Vital signs  | X  |   | X                           |              | X                  | X                  | X                             | X                             | X                  |  |                            |
| Fundoscopy e  | X  |   |                             |              |                    |                    |                               |                               | X                  |  |                            |
| MRI/CT scan for childhood cancer survivors                           |  |   |                             |              |                    |                    |                               |                               | X                  |  |                            |
| Trial drug dispensing  |  | X   | X                           |              | X                  | X                  | X                             | X                             |                    |  |                            |
| Trial drug training and administration f                  |  | X f  |                             |              |                    |                    |                               |                               |                    |  |                            |
| Dose titration instruction, if applicable                            |  |   | X                           | X            | X                  |                    |                               |                               |                    |  |                            |

| Timing  | Screening Visit  | V8  | Titration Period            |              |                    | Maintenance Period |                               |                               | End of Treatment   | Follow-up                                |                            |
|---|--|---|-----------------------------|--------------|--------------------|--------------------|-------------------------------|-------------------------------|--------------------|--|----------------------------|
|   |  |   | V9 week 4                   | V10 week 8   | V11 week 12        | V12 week 17        | V13 week 28                   | V14 week 38                   |                    | V15 week 52                              | V16 Safety                 |
| Procedure                                     | Screening Visit and Screening Procedures should be performed unless the subject can be dosed at V8 $\leq$ 8 weeks after TCH-306 V7. Subjects may not be re-screened if they failed eligibility criteria at V7. | $\leq$ 3 weeks after Screening Visit or TCH-306 V7 j | 3 weeks + 4-5 days after V8 | Remote visit | 4-5 days post dose | 4-5 days post dose | 1-3 days (8-75 hrs) post dose | 1-3 days (8-75 hrs) post dose | 4-5 days post dose | Remote visit, 14-16 days after last dose | 30-37 days after last dose |
| AE review, including injection site reactions |  |   | X                           | X            | X                  | X                  | X                             | X                             | X                  | X  |                            |
| Concomitant medication review                 |  |   | X                           | X            | X                  | X                  | X                             | X                             | X                  |  |                            |
| Participant diary review                      |  |   | X                           | X            | X                  | X                  | X                             | X                             | X                  |  |                            |
| Drug accountability                           |  |   |                             |              | X                  | X                  | X                             | X                             | X                  | X  |                            |

a Informed consent must be obtained before the start of any screening procedures unless performed as part of TCH-306 V7

b At V8, pregnancy is checked by urine testing only, at all other visits this is determined by serum

c Fasting required (except at the follow-up visit). Lab samples to be processed as described in the Laboratory Manual and shipped to central lab on the day of sampling

d DXA scan window is up to 1 week before or after visit. To be uploaded to central reader. If DXA scan will be performed at the same visit, DXA scan should be conducted before MRI/CT scan that uses contrast.

e Fundus photography is required for participants with a diagnosis of diabetes mellitus

f First dose administered at site; subsequent doses administered by patient on the same weekday. Diary to be handed out to participant with instruction to enter every dose taken

Inclusion and exclusion criteria should be reviewed at TCH-306 V7, at Screening Visit if performed, and at V8. Eligibility review is documented under V7 of TCH-306 in the EDC system

j If a subject was consented for TCH-306EXT after TCH-306 V7 and no Screening Visit was done, V8 must occur  $\leq$ 3 weeks after the date of consent AND  $\leq$ 8 weeks after V7

## 2. INTRODUCTION

[figure not shown]
### 2.1. TRIAL RATIONALE

The primary objective of this open-label extension trial is to assess the long-term safety of once-weekly lonapegsomatropin in adults with GHD who participated in trial [TCH-306](#). GHD in adults is associated with central adiposity, diminished lean muscle mass, decreased bone mass, and reduced quality of life ([Melmed 2019](#)). Growth hormone (GH) replacement therapy represents standard of care treatment that addresses multiple aspects of the condition ([Ho 2007](#), [Molitch 2011](#), [Yuen 2019](#), [Kim 2020](#)). This trial evaluates the safety of once-weekly lonapegsomatropin in adults with GHD over 52 weeks. The proposed length of this extension is 52 weeks is considered adequate to assess safety and is supported by the extensive clinical experience for lonapegsomatropin approved by the Food and Drug Administration (FDA) for the treatment of pediatric patients 1 year and older who weigh at least 11.5 kg and have growth failure due to inadequate secretion of endogenous growth hormone (GH). The doses used in pediatric patients are higher (approximately 2-6-fold based on weight) than used in adults with GHD.

### 2.2. BACKGROUND

Lonapegsomatropin (ACP-011, TransCon hGH) is a long-acting prodrug of somatropin (hGH), designed to maintain the same mode of action and distribution as daily somatropin products, but with a once-weekly injection. Lonapegsomatropin consists of a parent drug, somatropin, that is transiently conjugated to a methoxypolyethylene glycol (mPEG) carrier (4 × 10 kDa mPEG) via a proprietary TransCon Linker ([Figure 1](#)). The carrier has a shielding effect that minimizes renal excretion and receptor-mediated clearance of lonapegsomatropin. At physiologic pH and temperature, lonapegsomatropin releases fully active, unmodified hGH via autocleavage of the TransCon Linker in a controlled manner that follows first-order kinetics.

**Figure 1: Structure of Lonapegsomatropin (ACP-011)**

PEG10-OMe: 10 kDa methoxypolyethylene chain.

Please refer to the current version of the Investigator's Brochure for detailed information pertaining to lonapegsomatropin.

## 2.3. BENEFIT/RISK ASSESSMENT

In treatment of adults with GHD, lonapegsomatropin is an investigational long-acting prodrug of hGH with a proposed once-weekly dosing regimen designed to overcome the inconvenience and suboptimal compliance of daily hGH injections. The safety and efficacy profiles are anticipated to be comparable to currently approved hGH products for daily use, while maintaining similar exposure ( $C_{max}$  and weekly AUC). Moreover, the exposure to hGH over the weekly dosing interval is anticipated to enhance delivery of hGH into target tissues and optimize efficacy. Obviating the need for daily injections should increase compliance and therefore long-term efficacy, which would be of great benefit to adult patients with GHD. All participants will receive weekly lonapegsomatropin treatment during this trial. Lonapegsomatropin is approved by the FDA for treatment of pediatric GHD.

The safety of the participants will be monitored by the investigators as well as the medical monitors.

Stopping rules have been defined in the protocol. There are no high-risk procedures required and the measurement of the efficacy endpoint by dual-x-ray-absorptiometry (DXA) can be considered standard of care and is only associated with very low X-ray exposure.

In conclusion, the benefit-risk assessment for this trial is acceptable based on nonclinical, already gained clinical experience and safety data in the pediatric populations and the fact that no harming trial procedures are implemented.

More detailed information about the known and expected benefits and risks and reasonably expected AEs of lonapegsomatropin is found in the current version of the Investigator's Brochure, and in the prescribing information for Skytrofa®.

[figure not shown]
[figure not shown]
### 2.3.1. Risks Related to the COVID-19 Pandemic

Lonapegsomatropin is a long-acting prodrug that liberates somatropin and is believed not to cause immunosuppression. Therefore, the risk of participants being exposed to SARS-CoV-2 or suffering from COVID-19 due to treatment with lonapegsomatropin, will be similar to that of the general population. Participants and site staff involved in this trial are expected to act according to local guidelines, recommendations, national laws, local restrictions, and hospital procedures related to COVID-19, and hereby ensure keeping the risk of viral infection low. Decisions to adjust the trial conduct will be based on the risk assessment performed by the Sponsor. The risk assessment will, as applicable, include a risk assessment of each individual trial participant. In case of local COVID-19 outbreaks several mitigating actions can be applied to ensure patient safety and data integrity: Site visits can be replaced by remote contacts as phone calls or virtual meetings, safety lab and assessments can be done locally, and trial medication can be sent directly to the home of the participants.

### 2.3.2. Overall Benefit Risk Conclusion

Taking into account the measures taken to minimize risk to participants in this trial, the potential risks identified in association with *trial intervention* are justified by the anticipated benefits that may be afforded to participants with GHD.

### 3. OBJECTIVES AND ENDPOINTS

| Objectives  | Endpoints  |
|---|--|
| Primary  |  |
| 

To evaluate the safety of once-weekly lonapegsomatropin in adults with GHD previously treated in trial TCH-306

  | 
Safety endpoints as measured throughout the treatment period:
 

AEs

Laboratory values

Vital signs

Immunogenicity

12-lead ECGs

Fundoscopy

  |
| Secondary  |  |
| 

To evaluate the efficacy of once-weekly lonapegsomatropin in adults with GHD

   | 
At Week 52 (as assessed by DXA):
 

Trunk percent fat

Trunk fat mass

Total body lean mass

   |

## 4. TRIAL DESIGN

### 4.1. OVERALL DESIGN

This is a phase 3 open-label multicenter extension trial designed to evaluate the long-term safety and efficacy of lonapegsomatropin administered once-weekly. The trial participants are adults (males and females) with GHD having completed the treatment period in trial **TCH-306** (foresiGHt). Therefore, participants are either previously treated with lonapegsomatropin, a daily somatropin product, or placebo in trial TCH-306.

The trial duration will up to 60 weeks in total and consist of:

- Screening Period – up to 3 weeks starting at Screening Visit. A Screening Visit is not needed if all inclusion and no exclusion criteria were met at V7 and if V8 occurs  $\leq$ 8 weeks after V7.
- Treatment Period – (52 weeks), consisting of:
  - Dose Titration Period – 12 weeks, three visits
  - Dose Maintenance Period – 40 weeks, four visits
- Follow-up Treatment-free Period – (30-37 days/4-5 weeks), consisting of:
  - Two weeks after the last dose of trial drug: Collection of AEs remotely
  - 30-37 days after the last dose of trial drug: Samples for ADA and pregnancy test (for females of childbearing potential)

**Figure 2: Trial Design**

| Screening Period
(up to 3 weeks)           | Treatment Period (52 weeks)    |                           |                            |                                  |                 |                 |                 | Follow-Up Period
(4 weeks) |                                     |                              |
|---|--------------------------------|---------------------------|----------------------------|----------------------------------|-----------------|-----------------|-----------------|-------------------------------|-------------------------------------|------------------------------|
|   | Titration Period
(12 weeks) |                           |                            | Maintenance Period
(40 weeks) |                 |                 |                 |                               |                                     |                              |
| Once-weekly
Lonapegsomatropin
(N – 240) | Visit 8 (First Dose)
W1     | Visit 9 (Titration)
W4 | Visit 10 (Titration)
W8 | Visit 11 (Titration)
W12      | Visit 12
W17 | Visit 13
W28 | Visit 14
W38 | Visit 15
W52               | Follow-up: AEs/SAEs by phone
W54 | Follow-up: ADA sample
W56 |

### 4.2. SCIENTIFIC RATIONALE FOR TRIAL DESIGN

This trial design allows characterization of long-term safety and efficacy for lonapegsomatropin in adults with GHD (38 weeks in TCH-306 followed by 52 weeks in TCH-306EXT). Long-term safety and efficacy data are important because GH treatment for adults with GHD is typically a lifelong therapy.

### 4.3. JUSTIFICATION FOR DOSE

Due to the different hGH dose requirements, this trial includes individual doses depending on age, concomitant oral estrogen use, and trial drug tolerability as assessed by the investigator. The trial includes three dosing groups.

Participants will be initiated on a low dose, and the dose will slowly be increased to avoid adverse reactions as much as possible (Dose Titration Period) until the target maintenance dose is reached (Dose Maintenance Period).

### 4.4. END OF TRIAL DEFINITION

The end of the trial is defined as the date of the last visit of the last participant.

A participant is considered to have completed the trial if he/she has completed the treatment period.

## 5. TRIAL POPULATION

Prospective approval of protocol deviations to recruitment and enrollment criteria, also known as protocol waivers or exemptions, is not permitted. Inclusion and exclusion criteria should be reviewed at TCH-306 V7, at Screening Visit if performed, and at V8. Eligibility review is documented under V7 of TCH-306 in the EDC system.

### 5.1. INCLUSION CRITERIA

Participants are eligible to be included in the trial only if all the following criteria apply:

1. Signing of the trial specific informed consent
2. Completion of the treatment period and Visit 7 assessments of trial [TCH-306](#), including collection and upload of Visit 7 DXA scan
3. Fundoscopy at Visit 7 in trial TCH-306 without signs/symptoms of intracranial hypertension or diabetic retinopathy stage 2 / moderate or above

### 5.2. EXCLUSION CRITERIA

Participants are excluded from the trial if any of the following criteria apply:

1. Diabetes mellitus if any of the following are met:
  - a. Poorly controlled diabetes, defined as HbA1C higher than 7.5% according to central laboratory at Visit 7 in trial TCH-306
  - b. Use of diabetes mellitus drugs other than metformin and/or dipeptidyl peptidase-4 (DPP-4) inhibitors
2. Active malignant disease
3. Known history of hypersensitivity and/or idiosyncrasy to the investigational product (somatropin or excipients)
4. Female who is pregnant, plans to become pregnant, or is breastfeeding

5. Female participant of childbearing potential (i.e., fertile, following menarche and until becoming post-menopausal unless permanently sterile) not willing throughout the trial to use contraceptives as required by local law or practice. Details included in Appendix 4/Section 10.4 of this protocol
6. Male participant not willing throughout the trial to use contraceptives as required by local law or practice. Details included in Appendix 4/ Section 10.4 of this protocol
7. Any disease or condition that, in the judgement of the investigator, may make the participant unlikely to comply with the requirements of the protocol or any condition that presents undue risk from the investigational product or trial procedures
8. eGFR <60 mL/min/1.73m^2 determined based on Modification of Diet in Renal Disease (MDRD) equation using serum creatinine from the central laboratory at screening
9. Hepatic transaminases (ie, AST or ALT) >3 times the upper limit of normal according to the central laboratory at screening

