### **5.4. SCREEN FAILURES**

A screen failure occurs when a participant who consents to participate in the clinical trial is not subsequently entered in the trial. A minimal set of screen failure information to be collected in the eCRF includes age, sex, reason for screen failure, and any serious adverse event (SAE) reported. No re-screening of patients who screen fail will be allowed in the study. Patients who were screened and screen failed using Visit 7 assessments in TCH-306 may not be re-screened in a separate Screening Visit.

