## 7. DISCONTINUATION OF TRIAL INTERVENTION AND PARTICIPANT DISCONTINUATION/WITHDRAWAL

### 7.1. DISCONTINUATION OF TRIAL INTERVENTION

The investigator may discontinue treatment of a participant due to safety reasons e.g., AEs. If the participant agrees, the investigator may decide that the participant should continue the trial off treatment.

The investigator must stop the treatment for an individual participant in case of:

- Evidence of severe hypersensitivity to the trial drug
- Confirmed neutralizing anti-hGH antibodies
- Evidence of tumor growth or new onset malignancy
- Evidence of progression or new onset retinopathy
- Pregnancy

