## 8. TRIAL ASSESSMENTS AND PROCEDURES

- Participants will continue to be identified with the same 8-digit participant number as in trial **TCH-306**. Likewise, the site numbers will remain the same.
- Trial assessments, procedures and their timing are summarized in the SoA. Protocol waivers or exemptions are not allowed.
- All lab sampling should be drawn in the morning (6:00-10:00 AM) as participants are required to attend in a fasting status having consumed only water for the last 8 hours
- Immediate safety concerns should be discussed with the Sponsor immediately upon occurrence or awareness to determine if the participant should continue or discontinue trial intervention.
- Adherence to the trial requirements, including those specified in the SoA Section [1.2](#), is essential and required for trial conduct.
- All screening evaluations must be completed and reviewed to confirm that potential participants meet the eligibility criteria. The investigator will maintain a screening log to record details of all participants screened and to confirm eligibility or record reasons for screening failure, as applicable.
- Procedures conducted, results obtained and recorded in the case report form (CRF) as part of the participation in trial TCH-306 obtained before signing of the informed consent form (ICF) will be utilized for screening or baseline purposes in this trial.

- CCI [REDACTED] CI [REDACTED]  
[REDACTED]
- The maximum amount of blood collected from each participant over the duration of the trial, will not exceed 300 mL.
- A diary will be handed out to the participants at each site visit. The participants will be instructed to enter every injection with the dose, date, and time together with the injection site i.e., right thigh, right abdomen, right buttock, left thigh, left abdomen, left buttock.

[figure not shown]

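### When a Screening Visit is required because Visit 7 is more than 8 weeks old, the HbA1c and fundoscopy entry criteria still read only Visit 7, not the repeat results

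*Protocol*

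**What the plan says.** Section 4.1 and the Screening Visit column of the Schedule of Activities (section 1.2) waive the Screening Visit for a participant who is eligible at TCH-306 Visit 7 (V7) and has V8 within 8 weeks of it. Otherwise a Screening Visit is held. Fundoscopy and the safety laboratory tests are marked in its column, and Appendix 2 (section 10.2) includes HbA1c in the central laboratory panel. The V8 column allows at most 3 weeks from the Screening Visit or V7 to V8.

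Four entry criteria depend on a dated test result:

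- Exclusion 1a, under diabetes mellitus: HbA1c "higher than 7.5% according to central laboratory at Visit 7 in trial TCH-306".
- Inclusion 3: "Fundoscopy at Visit 7 in trial TCH-306 without signs/symptoms of intracranial hypertension or diabetic retinopathy stage 2 / moderate or above".
- Exclusion 8, eGFR: "using serum creatinine from the central laboratory at screening".
- Exclusion 9, AST or ALT: "according to the central laboratory at screening".

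Section 5 adds: "Inclusion and exclusion criteria should be reviewed at TCH-306 V7, at Screening Visit if performed, and at V8". Section 8 says that TCH-306 results obtained before consent "will be utilized for screening or baseline purposes in this trial".

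**The concern.** The schedule implies that beyond 8 weeks V7 data no longer suffice for entry, and it orders the tests again. Two of the four dated criteria follow that logic. The other two are fixed to the visit that the repeat was meant to replace, so a new result on the wrong side of the sponsor's own limit does not trigger the criterion that sets the limit.

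Safety is the primary objective, and section 10.3.5 gives glucose metabolism particular attention in sponsor monitoring. Retinopathy also matters after entry: section 7.1 makes "Evidence of progression or new onset retinopathy" a mandatory reason to stop treatment. That rule is not an entry criterion, and it may not resolve this case cleanly. Under section 9.3.1 the last fundoscopy before the first dose is the baseline, so retinopathy first seen at the Screening Visit becomes part of baseline, and it is open whether it then counts as new onset. The next scheduled fundoscopy is at Week 52.

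**Working it through.** There is no sample size or power figure to reproduce. The check compares the texts and then works out the timing.

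**Which result decides entry**

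| Criterion | No Screening Visit (V8 by day 56) | Screening Visit required (V8 from day 57) |
|---|---|---|
| Exclusion 8, eGFR | V7, serving as screening (section 8) | Screening Visit |
| Exclusion 9, AST/ALT | V7, serving as screening (section 8) | Screening Visit |
| Exclusion 1a, HbA1c | V7 | V7, although repeated |
| Inclusion 3, fundoscopy | V7 | V7, although repeated |

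The wording of exclusions 8 and 9 works on both routes. The wording of 1a and inclusion 3 works only on the first.

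**Age of the results at first dose.** Let V7 be day 0, V8 day D and the Screening Visit day S.

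- The Screening Visit is mandatory when D exceeds 8 × 7 = 56, so D ≥ 57.
- Age of the V7 HbA1c and fundoscopy at first dose: D − 0 = D ≥ 57 days. No upper limit is stated.
- The V8 column requires D − S ≤ 3 × 7 = 21, so the repeat results are at most 21 days old.
- S ≥ D − 21 ≥ 57 − 21 = 36. The results deciding eGFR and AST/ALT are thus at least 36 days more recent than those deciding HbA1c and fundoscopy.

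**Worked case for a participant with diabetes (HbA1c values are illustrations, not data).** V7 HbA1c is 7.4%; the Screening Visit on day 70 gives 8.5%; V8 is on day 84. The interval 84 − 70 = 14 days is within 21. Exclusion 1a reads 7.4%, which is 84 days old, and does not exclude. The 14-day-old value is above the limit but is not the one read.

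**Minor drafting note: V8 on days 22 to 56 (56 − 21 = 35 days).**

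- Consent at or before V7: the V8 column stops at day 21 if no Screening Visit is held, whereas section 4.1 needs none up to day 56. The texts are not reconciled.
- Consent after V7 and at most 21 days before V8: footnote j reconciles them.
- Consent after V7 but more than 21 days before V8: footnote j does not permit V8 without a Screening Visit, whereas section 4.1 says none is needed. The texts are again not reconciled.

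Holding a Screening Visit satisfies every sentence in all three groups.

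**The case against.** The best reply is that the protocol links Screening Visit results to eligibility in general terms. Section 5 has the criteria reviewed again at that visit, and section 8 requires screening evaluations to be completed and reviewed to confirm eligibility. This suggests leftover wording rather than a deliberate choice. That is fair on intent, but neither sentence rewrites 1a or inclusion 3. A site applying them literally re-reads V7.

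There are also other brakes, and a reader might wrongly infer that nothing, or only exclusion 7, can stop such an entry. Exclusion 7 lets the investigator exclude for undue risk, and recently seen retinopathy would be a clear basis. Exclusion 1b is not tied to a visit and acts if worsening glycaemia leads to a drug beyond metformin or a DPP-4 inhibitor. Section 8 requires immediate safety concerns to be discussed with the Sponsor. These stand, but they are discretionary or indirect, and none applies the 7.5% limit or the fundoscopy standard.

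Three further readings are tempting and not supported:

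- That the rule is unfairly one-sided because a V7 failure cannot be retested. Section 5.4 says so outright: "Patients who were screened and screen failed using Visit 7 assessments in TCH-306 may not be re-screened in a separate Screening Visit". This is a deliberate general rule and not part of the defect.
- That such entries would escape deviation reporting under SAP section 11.3. If no criterion is broken there is no eligibility deviation to report, so this adds no separate consequence.
- That the day 22 to 56 texts leave sites with no compliant path. They do not, and footnote j settles the matter for one of the three consent groups.

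**Conclusion.** The point holds as a wrong stated rule of modest weight. Followed literally, the protocol can admit a participant whose most recent pre-dose HbA1c or fundoscopy fails the sponsor's own limit, unless a discretionary or indirect safeguard acts. The timing is certain from the text: deciding results at least 57 days old, with repeats at most 21 days old available.

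The number affected is not given. The 220 TCH-306 completers in SAP section 4 are only a ceiling and say little. For HbA1c and retinopathy the exposed group is mainly participants with diabetes who were within limits at V7, needed a Screening Visit and crossed a limit in between. The intracranial hypertension part of inclusion 3 is not confined to diabetes.

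The conclusion assumes that the safety laboratory tests at the Screening Visit include the HbA1c listed in Appendix 2, and that the V7 tests were done on the day of V7. Nothing here affects the DXA endpoints or the baseline definitions, and the protocol tests no formal hypothesis (section 9.1).

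**What to change.** Amend two criteria:

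- Exclusion 1a: after the reference to Visit 7 in TCH-306, add *or, if performed, at the Screening Visit*.
- Inclusion 3: after the reference to Visit 7 in TCH-306, add *and, if performed, at the Screening Visit*.

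Both visits must then pass, which leaves the ban on re-screening V7 failures intact.

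For participants already enrolled, list any whose Screening Visit HbA1c was above 7.5% or whose Screening Visit fundoscopy would have failed inclusion 3. If enrolment has closed, this listing is the part that remains useful.

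As a tidy-up in the same amendment, state one rule for V8 on days 22 to 56 when consent was at or before V7, or after V7 but more than 21 days before V8. Align the V8 column, footnote j and section 4.1 with it.

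The cost is a few words in an amendment and no new test, since both are already scheduled at the Screening Visit. The downside is that a few participants who fail the repeat would be excluded. The tidy-up adds a visit for those two consent groups only if the sponsor chooses to require a Screening Visit there.
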